3.7.5.5.3 Barnes Akathisia Rating Scale

The BARS²⁹ consists of 4 items related to akathisia: objective observation of akathisia by the investigator, subjective feelings of restlessness by the subject, subjective distress due to akathisia, and global clinical assessment of akathisia. The first 3 items will be rated on a 4-point scale, with a score of zero representing absence of symptoms and a score of 3 representing a severe condition. The global clinical evaluation will be made on a 6-point scale, with zero representing absence of symptoms and a score of 5 representing severe akathisia. To complete this scale, subjects will be observed while they are seated and then standing for a minimum of 2 minutes in each position. Symptoms observed in other situations (eg, while engaged in neutral conversation or engaged in other activity) may also be rated. Subjective phenomena are to be elicited by direct questioning. Propranolol is not permitted within 12 hours of scale administration (see Section 4.1). Investigators are encouraged to delay scale administration until the required time frame has elapsed, if at all possible. However, if delaying administration of the scale is not feasible, the BARS should still be administered and the use of the medication documented, including a notation of the drug name, dose, and time of administration on

the eSource. The BARS global score is defined as the global clinical assessment of akathisia.

3.7.5.5.4 Sheehan Suicidality Tracking Scale

Suicidality will be monitored during the trial using the Sheehan-STS.³⁰ The Sheehan-STS is a prospective scale that assesses treatment-emergent suicidal thoughts and behaviors. Each item of the Sheehan-STS is scored on a 5-point Likert scale (0 = not at all; 1 = a little; 2 = moderate; 3 = very; and 4 = extremely). The Sheehan-STS can be analyzed as individual item scores, suicidal ideation subscale score, suicidal behavior subscale score, or total score. The trial will use the "Screening" and "Since Last Visit" versions of the scale. The "Screening" Sheehan-STS form will be completed at the screening visit to determine eligibility. Any subject with evidence of serious risk of suicide based on the Sheehan-STS, ie, a score of 3 or 4 on any one question 2 through 6 or 11 or a score of 2 or higher on any one questions 1a, 7 through 10, or 12, or who, in the opinion of the investigator, present a serious risk of suicide should be excluded from the trial (see Table 3.4.3-1). The "Since Last Visit" Sheehan-STS form will be completed at all other visits. The medical monitor should be contacted if a score of 3 or 4 on any one question 3 through 6 or 11 or a score of 2 or higher on any one questions 1a, 7 through 10, or 12, or 18, or if suicide results in death.

3.7.5.5.5 Mini-Mental State Examination

The MMSE³¹ is a brief practical test for assessing cognitive dysfunction. The test consists of 5 sections (orientation, registration, attention and calculation, recall, and language) and has a total possible score of 30. The MMSE is used for screening subjects (refer to Table 3.4.2-1) and is also to be completed at baseline and Week 12 or ET.

3.7.6 Pharmacokinetic/ Assessments

3.7.6.1 Pharmacokinetic Assessments

3.7.6.1.1 Pharmacokinetic Blood Samples

The PK samples will be collected at baseline and during Week 8 and Week 12 or ET visits. The samples will be collected at the same time as clinical laboratory sample collection for the designated trial visits, as applicable. Every possible effort should be made to collect PK samples at the same time at each visit. Furthermore, the subject should be advised to take the IMP at approximately the same time each day throughout the trial, but most importantly, prior to each PK sampling. The date and time of the last 2 doses of IMP prior to each sample draw, and the date and time of the actual blood draw

will be recorded on the eSource. Vital sign and ECG assessments should be completed before any blood samples are collected. All blood samples will be shipped to the testing facility for analysis. Detailed handling and shipping instructions are provided in Appendix 1.

3.7.7 End of Trial

The end of trial date is defined as the last date of contact or the date of final contact attempt from the post-treatment follow-up eSource page for the last subject completing or withdrawing from the trial.

3.7.8 Independent Data Monitoring Committee

This trial will be monitored by an independent DMC. The DMC will periodically monitor safety based on a predetermined schedule. In addition, an interim analysis of efficacy data is planned during the course of the trial, and will be performed by the independent DMC. The sponsor will remain blinded to the observed results of the interim analysis, and will only receive recommendations as per the interim analysis plan and DMC Charter. The DMC meetings will occur as outlined in the DMC Charter, but can be convened at any time at the discretion of the DMC chair or the trial medical officer. The details of the DMC structure and its roles and responsibilities will be documented in a DMC Charter.

3.7.9 Independent Adjudication Panel and Clinical Surveillance Team

The IAP will consist of medical experts from different specialties, independent from the sponsor or designee, who in collaboration with the CST at Syneos HealthTM will use external quality oversight methods to promote appropriate subject enrollment. Such methods will require sites to communicate certain aspects of subject data during the screening period to CST and the IAP, as detailed in the Operations Manual. Eligibility review must be completed for each subject and submitted to CST and the IAP per the Operations Manual. Subjects cannot be randomized until approval from CST and the IAP has been received. The investigator is responsible for ensuring that subjects are eligible for enrollment into the trial and for assessing subject safety throughout the trial. The IAP will provide an independent assessment of the subject's eligibility at time of enrollment and may request exclusion of a subject from entry into the trial.

3.8 Stopping Rules, Withdrawal Criteria, and Procedures

3.8.1 Entire Trial or Treatment Arm(s)

If the sponsor terminates or suspends the trial for any reason, prompt notification will be given to investigators, IRBs or IECs, and regulatory authorities in accordance with regulatory requirements.

3.8.2 Individual Site

Individual trial site participation may be discontinued by the sponsor, the investigator, or the IRB or IEC if judged to be necessary for medical, safety, regulatory, ethical or other reasons consistent with applicable laws, regulations, and GCP. The investigator will notify the sponsor promptly if the trial is terminated by the investigator or the IRB or IEC at the site.

3.8.3 Individual Subject Discontinuation

3.8.3.1 Treatment Discontinuation

After randomization, a subject may stop treatment permanently for a variety of reasons. Treatment discontinuations may be initiated by a subject who is not satisfied with treatment or may become medically necessary due to AEs, required treatment with a disallowed medication or therapy, or other issues, as determined by the investigator. However, each investigator must comprehensively review the circumstances and offer the subject options for continued treatment to the degree possible as described in Section 3.8.3.4. Refer to the Schedule of Assessments (Table 3.7-1) for a description of follow-up procedures.

3.8.3.2 Documenting Reasons for Treatment Discontinuation

If a subject discontinues the trial prematurely, the reason must be fully evaluated and recorded appropriately in eSource. If the subject is being withdrawn because of an AE, the AE should be indicated as the reason for withdrawal.

All subjects have the right to withdraw at any time during treatment without prejudice. The investigator can discontinue a subject's participation in the trial at any time if medically necessary. In addition, subjects meeting any of the following criteria must be withdrawn from the trial:

• Occurrence of any AE, intercurrent illness, or abnormality in a laboratory assessment that, in the opinion of the investigator, warrants the subject's permanent withdrawal from the trial

- Treatment with a prohibited concomitant medication other than the use of appropriate medications for the treatment of AEs under direction of the investigator, unless allowed after discussion with and approval by the medical monitor
- Subject noncompliance, defined as refusal or inability to adhere to the trial schedule or procedures (see Section 3.12, Subject Compliance)
- At the request of the subject, caregiver, legally acceptable representative, investigator, sponsor, or regulatory authority
- Subject becomes pregnant (see Section 5.5)
- Subject cannot tolerate the assigned dose of brexpiprazole (or matching placebo)
- Subject develops clinically significant agitation per investigator's judgment that cannot be adequately treated with allowed medications and poses a potential safety risk to the subject or others
- Subject is lost to follow-up
- Subject transfers from an institutionalized setting to a non-institutionalized setting, or vice versa. In case of a brief hospitalization, determination of subject eligibility to stay in the trial must be made based on subject safety by the investigator and medical monitor.

The medical monitor should be contacted if the Sheehan-STS score is 3 or 4 on any one question 3 through 6 or 11 or if the Sheehan-STS score is 2 or higher on any one questions 1a, 7 through 10, or 12, or 18, or if suicide results in death.

Subjects withdrawn prior to Week 12 must complete the Week 12 or ET evaluations at the time of withdrawal. In addition, all subjects who withdraw prematurely from the trial will be assessed 30 (+ 2) days after the last dose of the IMP for evaluation of safety. This assessment can be accomplished at a clinic visit at either the investigator's site or residential facility, as applicable. If a clinic visit is not possible, the subject should be assessed by telephone contact with the subject and a caregiver. In addition, for all subjects who terminate early from the trial, all attempts will be made to collect mortality data by telephone contact with the subject's caregiver at Week 16. Three attempts will be made to contact the subject's caregiver by telephone; in the event the site is unable to reach the subject's caregiver by telephone, the site will attempt to contact the subject's caregiver via certified mail or an alternative similar method where appropriate.

Meeting a screening exclusion criterion postrandomization does not require an automatic discontinuation of the subject. The investigator should assess the change for clinical significance, determine if an AE should be reported, and make a determination of subject continuation based on subject safety. The investigator will consult with the medical monitor to determine subject continuation in the trial.

3.8.3.3 Withdrawal of Consent

All subjects have the right to withdraw their consent from further participation in the trial at any time without prejudice. Subjects cannot withdraw consent for use of data already collected as part of the trial, but only for future participation. The investigator can also discontinue a subject's participation in the trial at any time if medically necessary. Unless the subject provides their written withdrawal of consent or there is other written documentation by the investigator confirming the subject's verbal intent to completely withdraw from the trial, subjects should be followed for all protocol-specified evaluations and assessments, if possible.

Complete withdrawal of consent requires a subject's refusal of ALL of the following methods of follow up (these methods of follow up will also be noted in the trial ICF):

- Participation in all follow-up procedures specified in the protocol (whether in-clinic, by telephone, or by an in-home visit).
- Participation in a subset of protocol specified follow-up procedures (by a frequency schedule and method, as agreed by subject and staff).
- Contact of the subject by trial personnel, even if only by telephone, to assess current medical condition, and obtain necessary medical or laboratory reports relevant to the trial's objectives.
- Contact of alternative person(s) who have been designated in source records as being available to discuss the subject's medical condition, even if only by telephone, mail, or e-mail (eg, family, spouse, partner, legal representative, friend, neighbor, or physician).
- Access to medical information from alternative sources (eg, hospital or clinic medical records, referring doctor's notes, public records, dialysis, transplantation or vital registries, social media sources).

Withdrawal of consent is a critical trial event and therefore should be approached with the same degree of importance and care as is used in initially obtaining informed consent. The reasons for a subject's intended withdrawal need to be completely understood, documented, and managed to protect the rights of the subject and the integrity of the trial. A subject may initially express their desire to discontinue IMP administration, which is not equivalent to a complete withdrawal of consent for further participation (see Section 3.8.3.1). A subject may, however, indicate that further trial participation is creating a burden on their work or social schedule. Therefore, the investigator should follow the procedures outlined in Section 3.8.3.2 to determine if the subject can continue participation in the trial if modifications to his or her treatment or Schedule of Assessments can be accommodated. Only subjects who withdraw their permission for all

of the above degrees of follow-up are considered to have completely withdrawn their consent to participate in the trial.

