3.8.3.4 Procedures to Encourage Continued Trial Participation

In all cases of impending IMP discontinuation or consent withdrawal, investigators will be instructed to meet and discuss with the subject their options of continuing in the trial, preferably on therapy. The investigator should ensure understanding and documentation of the reasons for the subject's desire to withdraw consent.

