3.10 Definition of Completed Subjects

The treatment period is defined as the time period during which subjects are evaluated for primary or secondary objectives of the trial irrespective of whether or not the subject actually consumed all doses of the IMP. Subjects who are evaluated at the last scheduled visit during the treatment period will be defined as trial completers. For purposes of this trial, subjects who complete Week 12 visit will be defined as trial completers.

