### 8.1.1 Primary Estimand

In order to support the primary objective of the trial, treatment effect will be estimated under hypothetical situation had no subjects discontinued early from treatment. Due to this strategy, the last collected efficacy assessment after premature trial discontinuation will be done only once at the Early Termination (ET) Visit. Every effort will be made to complete all the ET evaluations prior to administering any additional medications for the treatment of agitation or any other prohibited medications. In the case of terminal or lost to follow-up event, no ET evaluations would be expected, and only scheduled assessments performed before such an event would be used for the primary efficacy analysis. All collected efficacy assessments will be slotted as per the Visit Window Definition, and only one assessment per visit window will be used for the primary efficacy analysis. If there are multiple assessments available in the same window, the latest one will be used.

This trial seeks to clarify the efficacy of brexpiprazole in improving the CMAI total score in the idealistic scenario of full adherence to the assigned treatment in all subjects. In clinical trial practice, however, instances of non-adherence such as treatment discontinuation are likely to occur before the study endpoint (i.e., the Week 12 Visit for this trial). Given this consideration, the hypothetical estimand is the most appropriate for achieving the primary objective of the trial. The primary estimand is described by five attributes as follows.

- Target Population: Subjects with agitation associated with dementia of the Alzheimer's type who have met protocol inclusion/exclusion criteria

- Endpoint: Change from Baseline to Week 12 in the CMAI total score
- Intercurrent Events: Intercurrent events refer to premature treatment discontinuation (i.e., early dropout) prior to Week 12 attributable to adverse events or lack of efficacy or withdrawal of consent/assent or any other causes.
- Measure of Intervention effect: Difference in endpoint means between the brexipiprazole and placebo treatment arm.
- Treatment regimen: 2 or 3 mg daily for 12 weeks.

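### Assessments after a subject stops IMP are specified two ways, and the SAP does not bar off-drug CMAI scores from an estimate defined as if no one had stopped

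*Protocol*

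**What the plan says.** One set of sections keeps the subject in the visit schedule:

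- Protocol 3.8.3.3: unless consent is withdrawn completely, "subjects should be followed for all protocol-specified evaluations and assessments, if possible". It adds: "A subject may initially express their desire to discontinue IMP administration, which is not equivalent to a complete withdrawal of consent for further participation".
- Protocol 3.8.3.4: when a subject is about to stop IMP or withdraw consent, the investigator is to "discuss with the subject their options of continuing in the trial, preferably on therapy". Being on therapy is a preference, not a condition.
- Protocol 3.10: the treatment period is the time under evaluation, "irrespective of whether or not the subject actually consumed all doses of the IMP", and a subject who completes the Week 12 visit is a trial completer.

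Another set takes the subject out of the trial:

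- Protocol 3.1 and 3.2: a subject who cannot tolerate the assigned dose leaves the trial.
- Protocol 3.8.3.2, although headed as treatment discontinuation: "subjects meeting any of the following criteria must be withdrawn from the trial". The list covers adverse events that warrant it, prohibited medication, noncompliance, intolerance and a request by the subject, among others. Then: "Subjects withdrawn prior to Week 12 must complete the Week 12 or ET evaluations at the time of withdrawal". What remains is the 30-day safety contact and the Week 16 mortality call.
- SAP 8.1.1: the intercurrent event is treatment discontinuation, equated with early dropout, and "the last collected efficacy assessment after premature trial discontinuation will be done only once at the Early Termination (ET) Visit".

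For the data that enter the analysis, SAP 8.1.1 defines the effect as if no subject had stopped treatment early. Its estimator nevertheless uses observed data up to discontinuation from the trial, and SAP 8.1.3 includes all scheduled visits in the 12 weeks. Neither section conditions on being on IMP.

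**The concern.** Take a subject who stops IMP but agrees to keep coming. A site that follows 3.8.3.3 rates this subject off drug up to Week 12 and records a completer. A site that follows 3.8.3.2 does one ET rating and records a dropout.

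The SAP's estimand text assumes the second course, but its data rule admits the first. Under the first, an off-drug Week 12 score counts as an ordinary observation in a contrast meant to describe full adherence. The MNAR analyses in SAP 8.1.4 are organised by dropout reason and impute missing values. This subject has neither a dropout reason nor a missing Week 12 score. At stake are the meaning of the primary contrast, some dilution of it, and a completer percentage that depends on which section a site applied.

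**Working it through.** **Does another section settle it?** Protocol 3.8.3.1 sends the reader to Table 3.7-1 for follow-up. The table has a combined Week 12 or ET column, a follow-up column and a Week 16 column for early terminators, but no path for a subject off IMP and still in the trial. Section 3.8.3.3 refers to 3.8.3.2 for deciding whether a subject can continue with modified treatment or visits. Section 3.8.3.2 sets out no such procedure for a subject who has stopped IMP. The question stays open.

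**Inputs (SAP section 4).** Effect 6.5 points; SD 16.5; 2:1 allocation; initial N 300, maximum about 330; interim at about 255; two-sided alphas 0.015 and 0.035; dropout 12-13%; stated power 89% (fixed design, alpha 0.05) and 87% (group-sequential).

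**Reproducing the plan's power.** With N subjects in total, the information is I(N) = (N/3) / (1.5 × SD²), the form used in SAP 8.7.

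- Fixed design, N = 300: I = 100 / (1.5 × 272.25) = 0.2449. Then 6.5 × √I = 3.217, and Φ(3.217 − 1.960) = 0.896, against the stated 89%.
- Group-sequential: power = 1 − P(Z1 < 2.432, Z2 < 2.108), where the Z's have means 6.5 × √I and correlation √(N1/N2). With 300 evaluable at the end, it is 0.870-0.871 for interim sizes from 225 to 255, against the stated 87%.

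Both figures reproduce.

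**Ceiling on the number exposed.** 330 × 0.12 = 39.6 and 330 × 0.13 = 42.9, so 40-43 subjects.

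**Effect on the contrast.** Let d be the dropout rate, f the share of those subjects who stay to Week 12 off drug, and k the share of the 6.5 points they keep. The documents give neither f nor k. Assume equal d in both arms and that every dropout stopped IMP. Then

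contrast = 6.5 × (1 − d + d·f·k) / (1 − d + d·f), with 330 × (1 − d + d·f) Week 12 values.

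| Case | Week 12 values | Contrast, d = 12% / 13% | Group-sequential power |
|---|---|---|---|
| f = 0 (ET visit only) | 290 / 287 | 6.5 / 6.5 | 0.860 / 0.856 |
| f = 1, k = 1 | 330 | 6.5 / 6.5 | 0.901 |
| f = 1, k = 0.5 | 330 | 6.11 / 6.08 | 0.861 / 0.857 |
| f = 0.5, k = 0 | 310 / 309 | 6.09 / 6.05 | 0.836 / 0.829 |
| f = 1, k = 0 | 330 | 5.72 / 5.66 | 0.812 / 0.803 |

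The largest shift is 6.5 × 0.12 = 0.78 to 6.5 × 0.13 = 0.85, or about 0.8 point; the smallest is 0. If one in ten of these subjects stayed (d = 12.5%, f = 0.1, k = 0), the contrast is 6.5 × 0.875 / 0.8875 = 6.41, a shift of 0.09.

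This is a two-sample approximation at Week 12. It ignores what the MMRM borrows from earlier visits and any ET visit that falls in the Week 12 window.

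**The case against.** The sections can be read as consistent. Section 3.8.3.2 says must and covers subjects withdrawn from the trial; 3.8.3.3 says should, if possible, in a section about consent. Its statement on IMP is only that wishing to stop is not complete withdrawal of consent. A subject could have the ET visit and still consent to the 30-day and Week 16 contacts, and those could be the protocol-specified evaluations meant. SAP 8.1.1 reads it that way. For intolerance and the other listed reasons, the withdrawal route is explicit.

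Much of this stands. It limits the ambiguity to a subject who stops IMP, is not caught by a mandatory criterion and accepts visits. It does not remove it: 3.8.3.4 contemplates continuing in the trial without therapy being required, no section gives that subject a schedule, and the SAP's data rule would accept the scores.

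SAP 9.10 also tabulates, by week and arm, subjects receiving IMP and completers. A gap between the two would hint at a sizeable off-IMP group, but it is a net difference and does not classify subjects. SAP section 12, the list of summary tables, is not in the available text, so a disposition row for these subjects cannot be said to be absent.

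A reader might also infer that SAP 8.1.4 is defective because it misses these subjects, and that relabelling them as dropouts would cure it. That does not follow. Those methods impute missing values, and a subject with an observed Week 12 score has none to impute. The gap lies earlier, in which scores the primary analysis accepts.

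**Conclusion.** The inconsistency is real and reaches the primary analysis. Following Protocol 3.8.3.3 together with the data rules in SAP 8.1.1 and 8.1.3 can yield off-drug scores in an estimate defined as if nobody had stopped treatment.

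Its size is unknown and probably modest. The shift in the Week 12 contrast lies between 0 and about 0.8 point. The upper end (5.7 against 6.5 points; power about 0.81 against 0.86) requires every dropout to stay to Week 12 with no residual effect, at equal rates by arm. With half the effect kept, power is about 0.86, as under the ET-only course; with all of it kept, power rises to 0.90. More stopping on brexpiprazole than on placebo would change the upper limit.

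A reader might infer that 40-43 subjects are affected, or that the estimate must move by at least 0.4 point. The documents support neither. The 12-13% is total dropout in two earlier trials. It can include subjects lost to follow-up or withdrawing consent completely, who can give no Week 12 score under any reading, and most other reasons carry mandatory withdrawal. The 0.4 figure assumes that all stay and lose half the effect.

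**What to change.** 1. Reconcile Protocol 3.8.3.3, 3.8.3.4 and 3.10 with 3.1, 3.2, 3.8.3.2 and SAP 8.1.1, so that one assessment schedule applies after IMP stops. Which schedule that should be is for the sponsor to decide.
2. State in SAP 8.1.1 and 8.1.3 that IMP discontinuation sets the data cut for the hypothetical estimand, with the ET visit slotted by visit window as already planned. Any later off-IMP score is then missing in the primary MMRM and is covered by the MNAR analyses in 8.1.4 under the reason for stopping IMP.
3. In disposition, report subjects with a Week 12 visit but off IMP as a separate category by arm.

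The cost is a protocol clarification, a short SAP change and one table row. SAP 6.2 already uses an IMP end date record. The stated sample size and power do not change. The downside is that a few observed scores leave the primary analysis and the completer percentage may fall slightly.
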